7.7. Pharmacokinetic Assessments

7.7.1. Blood Sample Collection

Blood samples (~4 mL each) for plasma PK analysis of encorafenib, its metabolite (LHY746), binimetinib and the active metabolite of binimetinib (AR00426032) will be collected from all patients enrolled in the Safety Lead-in portion of the study as shown in [Table 12](#). If the high-dose regimen is determined to be safe and patients are randomized to the high-dose and standard-dose treatments in the Phase 2 portion of the study, PK samples will also be collected from all Phase 2 patients as shown in [Table 12](#). However, if the high-dose regimen is determined not to be safe in the Safety Lead-in, PK samples will be collected from all Phase 2 patients as shown in [Table 13](#) using a reduced sampling schedule.

In addition to PK samples stated above, blood samples for PK may be requested for patients experiencing unexpected or serious adverse events; with evidence of disease progression; or with other events where PK sampling is considered useful (upon agreement between investigator and Sponsor). More than 1 PK sample per patient may be collected throughout the study; however, the total blood volume of additional PK samples collected per patient should not exceed 20 mL (ie, no more than 5, 4 mL samples).

Study visits for PK sampling should be scheduled in the morning so that proper predose and postdose PK blood samples can be collected. On the PK visit days, the morning doses of encorafenib and binimetinib will be taken at the study site at approximately the same time, only after collecting the predose PK sample. Predose sampling information will include the date and exact time of the most recent previous dose of encorafenib and binimetinib (except Cycle 1 Day 1), including the dose amount taken. Postdose sampling information, only needed for days with postdose PK sampling (i.e., Cycle 1 Day 1 and Cycle 1 Day 15), will include the date and exact time of the morning dose, including the dose amount taken. Except for the Cycle 1 Day 1 PK samples, which have to be obtained on the scheduled day, other PK samples may be obtained \pm 1 day from the scheduled date.

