If vomiting occurs within 4 hours following study drug administration on the day of PK sampling, no additional study treatment will be taken to replace the material that has been vomited and it is recommended that no more PK samples be taken after the emesis occurs. Vomiting that occurs on Cycle 1 Day 1 and Day 15 will be noted in the PK eCRF. Further

doses should be administered with premedication with antiemetic medications. Cycle 1 Day 15 PK sampling that was compromised due to emesis will be repeated on Cycle 2 Day 1 after premedication with antiemetics.

Blood will be collected in accordance with institutional guidelines. Any sampling problems will be noted in the eCRF and on appropriate source documentation. Complete instructions for sample processing, handling and shipment will be provided in the Laboratory Manual.

CCI [REDACTED]

Table 12. Pharmacokinetic Blood Sample Timing in the Safety Lead-in Portion and in the Phase 2 Portion When the High Dose Regimen is Tested

Study Visit	Timing of Sample
Cycle 1 Day 1	
• 0.5 hours (\pm 5 min) postdose• 1.5 hours (\pm 5 min) postdose• 3 hours (\pm 10 min) postdose• 6 hours (\pm 20 min) postdose
Cycle 1 Day 15	
• Predose (within 30 minutes of dose)• 0.5 hours (\pm 5 min) postdose• 1.5 hours (\pm 5 min) postdose• 3 hours (\pm 10 min) postdose• 6 hours (\pm 20 min) postdose
Cycle 2 Day 1	
• Predose (within 30 minutes of dose)
Cycle 3 Day 1	
• Predose (within 30 minutes of dose)

Table 13. Pharmacokinetic Blood Sample Timing in the Phase 2 Portion When Only the Standard Dose Regimen is Tested

Study Visit	Timing of Sample
Cycle 1 Day 1	
• 1.5 hours (\pm 15 min) postdose
Cycle 2 Day 1 ¹	
• Predose (within 30 minutes of dose)• 1.5 hours (\pm 15 min) postdose
Cycle 3 Day 1	
• Predose (within 30 minutes of dose)• 1.5 hours (\pm 15 min) postdose

¹ Seven days of consecutive dosing at the starting doses (450 mg QD encorafenib + 45 mg BID binimetinib) are required prior to the intra-patient escalation (600 mg QD encorafenib + 45 mg BID binimetinib) and the escalation must start within 7 days of Cycle 2 Day 1 (see [Section 6.7.2.](#)). If the escalation occurs after Cycle 2 Day 1 the Cycle 2 Day 1 PK samples must be taken on the same day as the patient dose escalates.

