2. INTRODUCTION

This statistical analysis plan (SAP) provides the detailed methodology for summary and statistical analyses of the data collected in Study C4221006 (ARRAY-818-201). This document may modify the plans outlined in the protocol; however, any major modifications of the primary endpoint and key secondary endpoint definition or corresponding analyses will also be reflected in a protocol amendment.

The study plans to have two parts with Safety Lead-in followed by Phase 2. At the time of this document development, 3 dose-limiting toxicities (DLTs) have been observed in 9 evaluable patients enrolled in the Safety Lead-in of the study. The protocol defines the high-dose regimen of 300mg BID encorafenib + 45mg QD binimetinib combination therapy deemed not safe if 3 DLTs or more (ie, $\geq 33\%$) are observed in 9 evaluable patients in the Safety Lead-in. Therefore the study continues to Phase 2 without the high-dose regimen. The SAP version 2.0 is developed based on this study design scenario, ie, if the high-dose treatment is determined not to be safe in the Safety Lead-in, no patients will be enrolled into the high-dose arm, up to 100 patients will be enrolled into 2 cohorts in the standard-dose arm and no randomization will be used in the Phase 2 part of the study.

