6.3.1.1. Plasma Concentrations of Encorafenib, LHY746, Binimetinib and AR00426032

Plasma concentrations of encorafenib, LHY746, binimetinib and AR00426032 will be quantitated at the time points indicated in Table 5:

Table 5: Pharmacokinetic Blood Sampling Times

Study Visit	Timing of Sample	Allowed Window ^a
C1D1	0.5 hours postdose	±5 min
	1.5 hours postdose	±5 min
	3 hours postdose	±10 min
	6 hours postdose	±20 min
C1D15	Predose	-30 min
	0.5 hours postdose	±5 min
	1.5 hours postdose	±5 min
	3 hours postdose	±10 min
	6 hours postdose	±20 min
C2D1 ^b	Predose	-30 min
C3D1	Predose	-30 min

^a Predose samples must be within 30 minutes of, but before, the following dose.

^b When more sampling is performed on C2D1 due to emesis on C1D15, the sample times and windows will be the same as for C1D15.

All plasma concentration values of each analyte for each patient in the PK set will be included in the bioanalytical plasma concentration listings. Individual concentration records will be flagged for the affected visit if any of the following occur on the day of PK sampling:

- a. Patient had vomiting:
 - within 4 hours following study drug administration on the day of PK sampling for post-dose samples (C1D1, C1D15 and C2D1 when more sampling is performed on that day due to emesis on C1D15); or
 - at any time over the preceding 24 hours for pre-dose samples (C1D15, C2D1 and C3D1).
- b. Prescription dosing was not performed for at least 4 consecutive days prior to C1D15, C2D1 or C3D1).
- c. Patient received a higher or lower dose compared to planned treatment
- d. PK sampling time was outside the allowed window (as shown in [Table 5](#)) or the elapsed time was not calculable.

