The plasma concentrations of encorafenib, LHY746, binimetinib and AR00426032 will be summarized by dose, treatment cohort or arm and combined arms as applicable for all nominal time points, including predose (trough) concentrations for C2D1 and C3D1, using the following descriptive statistics: n (number of patients with non-missing values), m (number of non-zero [ie, > below the limit of quantification (BLQ)] concentrations), arithmetic mean, standard deviation, coefficient of variation (CV), geometric mean, geometric CV, minimum, median and maximum. An individual concentration-time data point may be excluded from the calculation of summary statistics if any of the above flags [a-d] apply. Concentrations below the BLQ will be set to zero for calculation of all summary statistics; geometric mean and geometric CV will set to missing if at least one BLQ value is included in the data being summarized. The arithmetic mean with standard deviation plasma concentration-versus-time profiles will be presented graphically for each analyte using both linear and semi-logarithmic scales by treatment arm on C1D1 and C1D15. Individual plasma concentration-time profiles (with median overlaid) will also be presented graphically using linear and semi-logarithmic scales by treatment arm and study day. For ease of presentation, nominal times will be used to present results in summary figures; for individual figures, actual times will be used.

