6.3.1.2. Plasma Pharmacokinetic Parameters for Encorafenib, LHY746, Binimetinib and AR00426032

Pharmacokinetic parameters for patients in the PK set will be determined by treatment arm for encorafenib, LHY746, binimetinib and AR00426032 when possible and appropriate.

The individual plasma concentration-time data for each analyte will be evaluated with noncompartmental analysis (NCA) using Phoenix WinNonlin®, version 8.0 or higher. Actual blood collection times and doses on the day of PK sampling will be used for PK calculations. All BLQ values before the observed maximum plasma concentration (C_{max}) will be set to 0; all BLQ values after C_{max} will be considered as missing.

The following parameters will be calculated for encorafenib, LHY746, binimetinib and AR00426032 on C1D1 and C1D15:

PK Parameter	Definition
AUC ₀₋₆	Area under the plasma concentration-time curve from zero to 6 hours after drug administration
AUC _{last}	Area under the plasma concentration-time curve from zero to the last measurable time point
AUC _{tau}	Area under the plasma concentration-time curve over a dosing interval (C1D15 only) To estimate AUC _{tau,ss} , the concentration measured at predose on C1D15 will be imputed as the concentration at the end of the dosing interval (ie, 12 or 24 hours, as appropriate) assuming steady-state has been attained
C _{max}	Maximum observed plasma concentration after drug administration
C _{min}	Minimum observed plasma concentration after drug administration
C _{trough}	Measured concentration at the end of a dosing interval
T _{max}	Time to reach C _{max}
T _{last}	Time of last PK sample
MR _{C_{max}}	Ratio of C _{max} values of the metabolite compared to parent, corrected for molecular weight, for AR00426032/ binimetinib and LHY746/Encorafenib
MR _{AUC_{last}}	Ratio of AUC _{last} values of the metabolite compared to parent, corrected for molecular weight, for AR00426032/ binimetinib and LHY746/Encorafenib
R _{AUC}	Accumulation ratio, calculated as: C1D15 AUC ₀₋₆ /C1D1 AUC ₀₋₆
R _{C_{max}}	Accumulation ratio, calculated as: C1D15 C _{max} /C1D1 C _{max}

C1D15 parameters will also be determined for C2D1 when more sampling is performed on that day due to emesis on C1D15.

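### The SAP's only PK schedule is the intensive one in Protocol Table 12; the reduced Table 13 schedule that governs Phase 2 without the high dose is missing

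*SAP*

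**What the plan says.** SAP section 2 reports 3 DLTs in 9 evaluable patients and draws the consequence: "Therefore the study continues to Phase 2 without the high-dose regimen". SAP v2.0 is built on that scenario.

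Protocol 7.7.1 sets the PK sampling for the same scenario: "if the high-dose regimen is determined not to be safe in the Safety Lead-in, PK samples will be collected from all Phase 2 patients" according to Table 13, "using a reduced sampling schedule". That table is titled "Pharmacokinetic Blood Sample Timing in the Phase 2 Portion When Only the Standard Dose Regimen is Tested". Its footnote 1 moves the C2D1 samples to the day of escalation if a patient goes to 600 mg after C2D1.

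SAP 6.3.1.1 has one schedule for all patients. Concentrations of the four analytes "will be quantitated at the time points indicated in Table 5". Flag d marks any sample taken outside the Table 5 window, and flag c marks a dose that differs from the planned one. On the effect of a flag, the SAP says: "An individual concentration-time data point may be excluded from the calculation of summary statistics if any of the above flags [a-d] apply".

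SAP 6.3.1.2 ties the noncompartmental parameters to two days: "The following parameters will be calculated for encorafenib, LHY746, binimetinib and AR00426032 on C1D1 and C1D15". Here a value carrying flag a, b or c is left out of the summaries without discretion.

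**The concern.** Characterising the PK of both drugs and their metabolites is a secondary objective. The Amendment 3 entry in Protocol Appendix 11 gives the purpose of the current Table 13: to see exposure at the 450 mg starting dose and after escalation to 600 mg. SAP v2.0 is linked to that same amendment and revised its list of PK parameters, but its schedule does not contain the Table 13 samples.

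At stake is whether the samples taken to show exposure after escalation have a planned summary, and whether first-dose samples are judged by the window under which sites collected them. A further question is which Phase 2 parameters a programmer should produce, since the list refers to a visit with no Phase 2 PK sampling.

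**Working it through.** No sample size, power or alpha figure is involved, so there is no figure of the plan to reproduce. The check compares the three schedules, then the parameter list against the samples that exist.

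**1. SAP Table 5 against Protocol Table 12.** Both have 4 samples on C1D1 (0.5, 1.5, 3, 6 h), 5 on C1D15 (predose, 0.5, 1.5, 3, 6 h), and a predose sample on each of C2D1 and C3D1: 4 + 5 + 1 + 1 = 11. Times and windows agree on 11 of 11.

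**2. Protocol Table 13 against SAP Table 5.**

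| Phase 2 sample (Protocol Table 13) | Window in protocol | In SAP Table 5? |
|---|---|---|
| C1D1 1.5 h | ±15 min | Yes, but ±5 min |
| C2D1 predose | within 30 min | Yes, same |
| C2D1 1.5 h | ±15 min | No |
| C3D1 predose | within 30 min | Yes, same |
| C3D1 1.5 h | ±15 min | No |

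So 2 of 5 match, 1 of 5 is held to a narrower window, and 2 of 5 are absent. In the other direction, 11 − 3 = 8 of the Table 5 samples are never scheduled in Phase 2. The SAP provides for C2D1 postdose samples only after emesis on C1D15, which is not a Phase 2 PK sampling day. If the two absent samples were treated as unscheduled, SAP 5.2.7 would keep them out of tables by nominal time point.

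**3. Compliant C1D1 samples that flag d would catch.** These are samples more than 5 and up to 15 min off nominal. The documents give no sampling-time data, so the spread is an assumption.

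- Uniform over ±15 min: (15 − 5)/15 = 0.67.
- Normal around nominal with standard deviation σ, truncated at ±15 min: share = 1 − [Φ(5/σ) − Φ(−5/σ)] / [Φ(15/σ) − Φ(−15/σ)].

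| σ (min) | 2 | 3 | 5 | 7.5 | 10 |
|---|---|---|---|---|---|
| Share flagged | 1% | 10% | 32% | 48% | 56% |

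For σ = 5: 1 − 0.683/0.997 = 0.315.

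**4. Parameters obtainable in Phase 2.**

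- All C1D15 parameters, including AUCtau: no C1D15 sample.
- RAUC and RCmax: both need C1D15 values.
- AUC0-6 on C1D1: not obtainable from one sample at 1.5 h.
- Cmax, Tmax, Tlast, AUClast and the metabolite ratios on C1D1: can formally be output from one sample, but carry no useful meaning.
- Ctrough: the predose samples on C2D1 and C3D1 could supply it, but the list covers only C1D1 and C1D15.

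**5. Escalation day.** Under footnote 1 of Protocol Table 13, the C2D1 predose sample reflects 450 mg and the 1.5 h sample follows the first 600 mg dose. The SAP's PK section does not address this. Flag c does not say whether escalation directed by the protocol counts as a dose different from planned.

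**The case against.** The strongest reply is that little would go wrong in practice.

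- SAP 6.3.1.1 lists every concentration, so a reader who infers that the C2D1 and C3D1 1.5 h samples are lost goes too far.
- The same section summarises concentrations by dose at all nominal time points, which can be read to include those of Protocol Table 13. Protocol 8.4.4 also asks for concentration summaries by dose and arm.
- Flagged concentrations may, not must, be excluded. SAP 5.3.2 sets a value to missing for a timing deviation only when the deviation is judged serious enough. The documents do not support a claim that valid first-dose samples will be discarded.
- SAP 6.3.1.2 and Protocol 8.4.4 limit the parameters to what is feasible and appropriate. The Phase 2 values would simply not be produced, and no wrong estimate follows.
- Sparse samples can feed the separate population PK analysis.

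Most of this stands as a limit on the consequences. It does not remove the contradiction. The only schedule in the SAP is the wrong one for Phase 2, flag d applies its narrower window, and the feasibility wording supplies neither the right schedule nor the right window. SAP 6.3.1.3 still describes the population PK analysis in terms of twice-daily high-dose encorafenib and reports it outside the main CSR, so it is not a stated replacement.

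**Conclusion.** The SAP's PK schedule and parameter list are wrong as written for the Phase 2 being run. Three of the 5 scheduled samples per patient are affected: 2 have no explicit summary plan and 1 is held to a window narrower than the protocol's. The C2D1 and C3D1 predose samples are handled correctly, and Table 5 is right for the Safety Lead-in.

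Two stronger readings should be avoided. One is that all properly collected Phase 2 samples are flagged or unplanned; the comparison shows otherwise. The other is that two thirds of C1D1 samples would be flagged. That is the highest of the cases computed and rests on uniform timing; the assumed spreads give about 1% to 67%, and the true share is unknown. It is also accurate to call the two 1.5 h samples the only *scheduled* postdose data after escalation, because Protocol 7.7.1 allows extra samples on request.

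The effect is confined to the descriptive, secondary PK objective. The primary endpoint, BMRR, is not touched. The point should be corrected but does not threaten the trial's main conclusion.

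**What to change.** - Label SAP Table 5 and the C1D1/C1D15 noncompartmental parameter list as applying to the Safety Lead-in only.
- Add a Phase 2 table that copies Protocol Table 13, with its ±15 min postdose window and footnote 1 on moving the C2D1 samples to the escalation day.
- Apply flag d by study part, each against its own table.
- State that escalation directed by the protocol does not trigger flag c, for concentrations or for parameters.
- Summarise Phase 2 predose and 1.5 h concentrations by visit and by the encorafenib dose each sample reflects. On the escalation day, predose belongs to the dose before escalation and 1.5 h to the dose after it.

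The cost is SAP text and table shells. No new samples, visits or patients are needed. With the change, all 5 scheduled Phase 2 samples become planned time points, and none is flagged for timing when taken within the protocol's limits.

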6.3.1.2. Plasma Pharmacokinetic Parameters for Encorafenib, LHY746, Binimetinib and AR00426032

Pharmacokinetic parameters for patients in the PK set will be determined by treatment arm for encorafenib, LHY746, binimetinib and AR00426032 when possible and appropriate.

The individual plasma concentration-time data for each analyte will be evaluated with noncompartmental analysis (NCA) using Phoenix WinNonlin®, version 8.0 or higher. Actual blood collection times and doses on the day of PK sampling will be used for PK calculations. All BLQ values before the observed maximum plasma concentration (C_{max}) will be set to 0; all BLQ values after C_{max} will be considered as missing.

The following parameters will be calculated for encorafenib, LHY746, binimetinib and AR00426032 on C1D1 and C1D15:

PK Parameter	Definition
AUC ₀₋₆	Area under the plasma concentration-time curve from zero to 6 hours after drug administration
AUC _{last}	Area under the plasma concentration-time curve from zero to the last measurable time point
AUC _{tau}	Area under the plasma concentration-time curve over a dosing interval (C1D15 only) To estimate AUC _{tau,ss} , the concentration measured at predose on C1D15 will be imputed as the concentration at the end of the dosing interval (ie, 12 or 24 hours, as appropriate) assuming steady-state has been attained
C _{max}	Maximum observed plasma concentration after drug administration
C _{min}	Minimum observed plasma concentration after drug administration
C _{trough}	Measured concentration at the end of a dosing interval
T _{max}	Time to reach C _{max}
T _{last}	Time of last PK sample
MR _{C_{max}}	Ratio of C _{max} values of the metabolite compared to parent, corrected for molecular weight, for AR00426032/ binimetinib and LHY746/Encorafenib
MR _{AUC_{last}}	Ratio of AUC _{last} values of the metabolite compared to parent, corrected for molecular weight, for AR00426032/ binimetinib and LHY746/Encorafenib
R _{AUC}	Accumulation ratio, calculated as: C1D15 AUC ₀₋₆ /C1D1 AUC ₀₋₆
R _{C_{max}}	Accumulation ratio, calculated as: C1D15 C _{max} /C1D1 C _{max}

C1D15 parameters will also be determined for C2D1 when more sampling is performed on that day due to emesis on C1D15.

The area under the curve (AUC) parameters will be calculated according to the linear-up log-down trapezoidal rule. All AUC, C_{max}, C_{min}, and C_{trough} values (AUC_{last}/D, AUC₀₋₆/D, AUC_{tau}/D, C_{max}/D, C_{min}/D and C_{trough}/D) will also be provided as dose-normalized values. Additional PK parameters may be calculated at the discretion of the pharmacokineticist.

All PK parameter values of each analyte will be presented in data listings by dose, treatment cohort or arm, cycle and study day. Individual PK records will be flagged for the affected visit and/or parameter if any of the following occur:

- a. Patient had vomiting:
 - within 4 hours following study drug administration on the day of PK sampling for post-dose samples (C1D1, C1D15 and C2D1 when more sampling is performed on that day due to emesis on C1D15); or
 - at any time over the preceding 24 hours for pre-dose samples (C1D15, C2D1 and C3D1).
- b. Prescription dosing was not performed for at least 4 consecutive days prior to C1D15, C2D1 or C3D1).
- c. Patient received a higher or lower dose compared to planned treatment for the related analytes.

Each parameter for each analyte will be summarized in tables by dose, treatment cohort or arm and combined arms as appropriate, cycle and study day using the following descriptive statistics: n, arithmetic mean, standard deviation, CV, geometric mean, geometric CV, minimum, median and maximum. Summary descriptive statistics for in-text summary tables will include geometric mean with geometric CV for AUC, AUC/D, C_{max}, C_{max}/D, and RAUC. For T_{last} and T_{max} values, median, minimum and maximum will be presented. Pharmacokinetic parameters will be excluded from the calculation of summary statistics if any of the above flags [a-c] apply.

6.3.1.3. Other PK Analysis

A separate population PK analysis with exposure-response analyses, if appropriate, will be conducted to further establish the PK for high daily dose encorafenib in BID administration. Details of the analyses will be included in a PK analysis plan and results will be presented separately from the main clinical study report (CSR).

CCI

CCI [REDACTED]

[REDACTED]

[REDACTED]

[REDACTED]

[REDACTED]

[REDACTED]

[REDACTED]

CCI [REDACTED]

[REDACTED]

- [REDACTED]

- [REDACTED]

[REDACTED]

[REDACTED]

6.5. Baseline and Other Summaries and Analyses

6.5.1. Baseline Summaries

The following analyses will be performed overall on the Dose-determining Set for the Safety Lead-in, and on the FAS by cohort and overall for the Phase 2.

[REDACTED]

[REDACTED]

